6 QUALITATIVE EVALUATION OF SUBJECTIVE CAPABILITIES AND QUALITY OF LIFE

On each visit a qualitative evaluation will be performed based on individual- and group interviews to evaluate how men find ADT and exercise affecting their quality of life and how they perceive the intervention as a means to increase their physical activity. On the interviews information will be collected on:

1. How men on ADT perceive their quality of life and what is their subjective definition of quality of life?
 - What kind of side-effects they have had from ADT, how they cope with them in everyday life and how cancer, ADT and ADT side-effects have affected their quality of life?
 - What role exercise has had in their lives before prostate cancer and after it, and how the amount of exercise is tied to their perceived quality of life?

2. What kind of opportunities and obstacles of exercise the participants find in their lives?
 - How men in the supervised exercise group think the intervention will affect their exercise activity in the future? Can supervised exercise help to overcome obstacles for exercising?
 - How men in the non-supervised exercise group cope with obstacles for exercise?

Baseline interview, before the study randomization: A group of 10 men are interviewed before randomization to the exercise groups. The goal is to find how participants expect the intervention to affect their activity and quality of life before they know in which group they will participate.

Second interview at the first control visit: Men in the supervised exercise group are interviewed about the role of their group and supervision on their exercise activity and perceived quality of life. Non-supervised group is interviewed how they have managed to follow the given exercise program and how it has affected their quality of life. All men are asked how they think their exercise habits would have differed had they been randomized to the other intervention group. Additionally their views about how they will be able to carry on exercising will be asked.

Third interview at the second control visit: The questions will evaluate how men have carried on with the exercise; have they been able to increase it or has it rather decreased; have the men found that the exercise intervention has affected their quality of life.

7 STUDY OUTCOMES AND STATISTICAL ANALYSIS

Primary outcomes:

- Daily total activity, measured during the entire course of study with wrist activity monitor in metabolic equivalents of task (MET) units
- Fasting plasma cholesterol, LDL, HDL and triglycerides, measured at baseline and again at the 1st and 2nd control visits
- Fasting plasma glucose and glycated haemoglobin (HbA1C), measured at baseline and again at the 1st and 2nd control visits
- Overall quality of life and prostate cancer-specific quality of life, measured with validated Finnish versions of EORTC QLQ-C30 v.3.0 ja EORTC QLQ-PR25 at baseline and at each control visit

Secondary outcomes:

- Change in daily activity after the end of supervised group exercise intervention; difference compared to the non-supervised group. Measured with wrist activity monitor in MET units
- Body mass composition, bioimpedance-based measurement of lean body mass, fat mass and skeletal mass as percentage of total body mass measured with TANITA MC-780 device

- Blood pressure level, measured at baseline and each control visit
- Subjective effect of exercise on quality of life and perceived adverse effects of ADT, as based on qualitative interviews

Long-term follow-up

The participants are followed via patient files and national health care registries. Outcomes to be followed are:

- Time from baseline to castration resistance (progression of prostate cancer despite ADT as evidenced by constantly rising PSA or radiological disease progression)
- Bone fractures
- Diagnosis of memory impairment
- Diagnosis of diabetes mellitus
- Diagnosis of cardiovascular disease
- Prostate cancer death
- Death due to any cause

Statistical analysis

All comparisons are done between the supervised and non-supervised exercise arms. Medians of daily activity (in MET units) and quantitative quality of life (as points from the EORTC surveys) at baseline and at each control visit are compared with either Mann-Whitney U-test or Student's t-test depending on normality of the data distribution. Difference in medians of plasma lipid parameters and glucose parameters are analyzed similarly.

Of the secondary outcomes median time to castration resistance and death are compared between the trial arms using Kaplan-Meier analysis and log-rank test. Analysis for risks of castration resistance, death, prostate cancer death, cardiovascular disease, bone fracture and memory impairment will be analysed using Cox regression with months from the study randomization as the time metric. The regression model will be adjusted for the study arm, age at baseline, time between prostate cancer diagnosis and randomization, ADT method and the time on ADT before participating in the trial.

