2 STUDY GOALS

[figure not shown]
The study compares effects of supervised and unsupervised exercise on plasma lipid parameters (total cholesterol, LDL, HDL and triglycerides) and glucose levels (fasting plasma glucose, glycated hemoglobin), overall quality of life and on average daily exercise activity in men with prostate cancer and under ADT. As secondary outcome we will study effect on continued exercise activity after the intervention, changes in body composition, blood pressure and risk of fractures, castration resistance as well as death due to prostate cancer and due to any cause.

Study hypothesis is that supervised exercise will improve quality of life, lipid and glucose parameters and increase daily exercise activity more than non-supervised exercise. We also expect higher continued exercise activity, greater changes in body composition and blood pressure and lowered risk of fractures and death in the supervised exercise group.

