3 STUDY SETTING

This is a randomized, controlled clinical trial. The study aims to recruit 40 men on ADT for prostate cancer. This will be a pilot study to estimate effect sizes in Finnish population to inform further larger trial. For this reason the sample size will be smaller compared to previous studies on the topic (10,11) and no power calculation is performed yet.

Figure: Study flow chart

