5 INTERVENTION

All participants attend introductory lecture, where a urologist informs them about adverse effects of ADT and positive effects of exercise during ADT, exercise instructor gives advice for training both at home and in the gym and nutritional therapist tells about nutrition to overcome adverse effects of ADT and support training.

After the introductory lecture the participants are randomized 1:1 to either the supervised or non-supervised exercise group (Figure). Men in the supervised group participate in progressive group exercise sessions twice a week for total of 12 weeks at the Varala sports academy in Tampere, Finland. Each exercise session includes both aerobic and resistance training targeting all major muscle groups (Additional document I, exercise program). The non-supervised group will exercise independently for 12 weeks according to the instructions given at the introductory lecture. The first control visit will be after this first period of 12 weeks of exercise.

After the first follow-up visit both groups will continue non-supervised exercise for 12 weeks, after which the second control visit will be arranged. Special focus on the second control visit is to see how many in each group has been able to carry on active exercising, i.e. has the intervention promoted long-term change in exercise activity.

Both study groups will be given Polar wrist activity monitors to be used 24 h/day for the entire course of the study.

All participants are asked to fill validated quality of life surveys EORTC QLQC-30 (overall quality of life) and EORTC QLQC-PR25 (prostate cancer-specific quality of life) at baseline and again at 1st and 2nd control visits. Plasma lipid and glucose parameters, blood pressure and body composition will be measured at each of these visits.

At each visit a separate blood sample is taken and stored for future measurement of biomarkers associated with prostate cancer progression, glucose and lipid metabolism and effects of exercise.

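### Continued activity is hypothesised as a level but listed as a change after supervision ends; the planned second-visit comparison, which would test the level, is not named as its analysis

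*Combined protocol and SAP*

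**What the plan says.** All references are to the combined protocol and SAP.

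- **Aim and hypothesis (section 2).** "As secondary outcome we will study effect on continued exercise activity after the intervention". The hypothesis for the supervised arm is "We also expect higher continued exercise activity". Section 2 also expects supervision to raise daily activity more than unsupervised exercise does.
- **Outcome (section 7, secondary outcomes).** "Change in daily activity after the end of supervised group exercise intervention; difference compared to the non-supervised group", measured by wrist monitor in MET units. Neither a start value nor an end window is given.
- **Timing (section 5).** Supervision lasts 12 weeks and the first control visit follows. "After the first follow-up visit both groups will continue non-supervised exercise for 12 weeks", and then the second control visit takes place. The focus of that visit is to "see how many in each group has been able to carry on active exercising", glossed as "i.e. has the intervention promoted long-term change in exercise activity". No threshold defines a man who has carried on.
- **Data (section 5).** "Both study groups will be given Polar wrist activity monitors to be used 24 h/day for the entire course of the study".
- **Analysis (section 7).** Daily activity is a primary outcome. It is compared between arms at baseline and at each control visit by Mann-Whitney U-test or Student's t-test, without adjustment. No test is named for the change, and the paragraph on analysis of secondary outcomes covers time-to-event outcomes only.
- **Purpose (section 3).** "This will be a pilot study to estimate effect sizes in Finnish population to inform further larger trial".

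**The concern.** The hypothesis asks whether supervised men are more active than controls once supervision has stopped. A change counted from the end of supervision asks something else: whether the difference between arms grew or shrank after week 12. If the trial works as section 2 expects, supervised men enter the second period ahead, and the change score can favour them only if that lead grows without supervision.

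Since the pilot is meant to supply effect sizes for a larger trial, the sign and definition of the estimate matter more than its p-value. If the week-12 change were carried forward as the continued-activity effect, a partly kept advantage would be passed on as negative and a fully kept one as zero. With two unlinked results that can differ in sign, the choice of which one answers the hypothesis is also left until the data are seen.

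**Working it through.** The plan states no SD, effect size, correlation or power, so there is no figure of its own to reproduce.

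**Inputs from the documents.** 40 men randomised 1:1, so 20 per arm; supervision ends at week 12; second control visit at week 24.

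**Assumed inputs.** Activity in SD units, correlation between time points 0.5 / 0.7 / 0.8, two-sided 0.05 t-tests, no dropout, equal expected baselines through randomisation. The working is in means; the plan may use ranks instead.

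**Step 1, what each reading estimates.** Let S and C be the arm means, D12 = S12 - C12 and D24 = S24 - C24.

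- Change from week 12: (S24 - S12) - (C24 - C12) = D24 - D12.
- Change from baseline, or level at week 24: D24.

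Write D24 = r × D12, where r is the share of the advantage kept. The week-12 change is then (r - 1) × D12. For D12 > 0 it is negative for every r below 1 and zero at r = 1. The control arm's own trend cancels. With D12 = 0.8 SD (assumed):

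| r | Change from week 12 | Week-24 level |
|---|---|---|
| 0 | -0.80 | 0.00 |
| 0.5 | -0.40 | +0.40 |
| 1 | 0.00 | +0.80 |
| 1.25 | +0.20 | +1.00 |

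What matters is the gap between arms, not the supervised men's own gain. If gains at week 12 are 3 v 1 and 80% v 20% is kept, D12 = 2, D24 = 2.4 - 0.2 = 2.2 and the change is +0.2, although supervised men lost some of their gain.

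**Step 2, how often the two results differ** (simulation, 20,000 replicates; correlations 0.5 / 0.7 / 0.8).

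| Gap, week 12 to 24 | Opposite signs | Change significant for control | Unadjusted level significant for supervision | Both significant, opposite directions |
|---|---|---|---|---|
| 0.7 to 0.3 | 73 / 78 / 80% | 24 / 35 / 50% | about 15% | 0.9 / 2.4 / 4.6% |
| 0.5 to 0.3 | 58 / 63 / 68% | not tabulated | not tabulated | 1% or less |

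With full retention (0.7 to 0.7) the change averages 0 and is significant for supervision in about 2.5% of trials, its chance rate. The unadjusted week-24 comparison is significant in 58%, and the baseline-adjusted one in 69 / 85 / 94%.

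**Step 3, precision of the week-24 comparison.** Unadjusted SE = sqrt(2/20) = 0.316. Adjusted for baseline, the simulated SE is 0.278 / 0.229 / 0.192. The equivalent unadjusted size is 20 × (0.316/SE)² = 26 / 38 / 54 men per arm.

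**Step 4, whether a mean over weeks 13 to 24 would serve instead.** Suppose the gap declines linearly from 0.7 at week 12 to 0 at week 24. At week t it is 0.7 × (24 - t)/12, and its mean over weeks 13 to 24 is 0.7 × 66/144 = +0.32. The window mean shows an advantage when none is left at the second visit.

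**The case against.** The strongest reply is that the plan already answers the level question. Daily activity over the whole study is a primary outcome and is compared between arms at the second control visit, so retained benefit would be seen. This stands, and it limits the harm. It does not remove the point, because nothing names that comparison as the analysis of continued activity.

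A second reply is that a change after supervision is a legitimate quantity. Zero under full retention is then the right answer to whether the gap shrank, and opposite signs are not a contradiction. This also stands: the change should be kept, as a measure of loss, but it does not test the section 2 hypothesis.

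A reader might infer that the outcome has no time anchor at all. The documents do not support that. The wording refers to the end of supervision, section 5 places that end at week 12, and week 12 is the natural reading. The section 5 gloss, "i.e. has the intervention promoted long-term change in exercise activity", leaves a baseline reading open, under which the sign problem disappears. The fair statement is that the reference value is not spelled out.

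Last, the opposite-sign rates follow from assuming that the gap shrinks but stays positive, and two significant results in opposite directions are rare. Both observations are correct. The case rests on what is being estimated, not on those rates.

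**Conclusion.** The point holds as a mismatch between hypothesis and listed outcome. Read from week 12, the outcome measures loss after supervision. Its sign behaviour follows from algebra and needs only a positive gap at week 12, which section 2 itself predicts. Every magnitude above is an assumption.

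Two stronger readings do not hold. One is that the trial would miss a retained benefit: the second-visit comparison is planned and the monitor data are collected. The other is that the plan will report the change score as the effect of continued activity: no section says so, and the harm arises only if someone uses it that way.

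This is a minor point, worth correcting because the change is cheap and because baseline adjustment also improves precision, from an SE of 0.316 to between 0.278 and 0.192 SD at the assumed correlations.

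**What to change.** 1. In section 7, name the between-arm difference in daily activity at the second control visit as the analysis of the continued-activity hypothesis. Take it from monitor data in a short, stated window ending at week 24, and adjust it for the baseline activity that the plan already records.
2. Keep the week-12-to-24 change, with its start point stated, as a separate measure of loss after supervision.
3. Do not use the mean over all of weeks 13 to 24 as the sole measure, for the reason shown in step 4 of the working.

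The cost is about one sentence in the outcome list and one in the analysis text, with no new outcome measure. Baseline monitor wear should precede randomisation. Section 5 does not say when monitors are issued, so a few days of earlier wear may be needed.

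### The primary activity outcome is recorded continuously for 24 weeks, but the plan does not say which days enter the comparison at each control visit

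*Combined protocol and SAP*

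**What the plan says.** Section 2 (Study goals) asks about the effect of supervision "on average daily exercise activity in men with prostate cancer and under ADT". Section 5 (Intervention) gives monitors to both groups, "to be used 24 h/day for the entire course of the study". Section 7 lists as its first primary outcome "Daily total activity, measured during the entire course of study with wrist activity monitor in metabolic equivalents of task (MET) units". The lipid, glucose and quality-of-life outcomes in the same list are instead tied to baseline and the two control visits.

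The statistical analysis paragraph of section 7 is the only place that says how primary activity is compared. It takes medians of "daily activity (in MET units) and quantitative quality of life (as points from the EORTC surveys) at baseline and at each control visit" and tests them between arms by Mann-Whitney or Student's t, depending on normality. It gives no averaging window, valid-day or wear-time rule, period mean, repeated-measures model or baseline adjustment.

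Section 7 also lists a secondary outcome: the change in activity once supervised sessions end, compared between arms and measured by the same monitor. Its summary is not defined either.

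**The concern.** The goal and the outcome definition describe an average over a period. The analysis sentence places activity beside a questionnaire score and ties both to visits. An analyst could follow it with the visit day, the week before the visit or the 12 weeks before it. These are different quantities with different variances. If the choice is left open, it can be made after up to 168 days of data per man have been seen.

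Two things are at stake. One is precision on a primary outcome with about 20 men per arm. The other is the purpose stated in section 3, which is to supply effect sizes for a larger trial. An effect size and SD for a visit-day value would not carry over to average daily activity. A single-day value has a further weakness. Supervised sessions run twice a week in one arm only, so that arm's value would depend on whether the chosen day was a session day.

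**Working it through.** The plan states no power, SD or detectable difference (section 3 says that no power calculation has been done), so there is no figure to reproduce.

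**Inputs from the documents.** 40 men randomised 1:1, so 20 per arm if recruitment is complete. Two periods of 12 weeks. On the first visit, section 5 says: "The first control visit will be after this first period of 12 weeks of exercise". The second visit follows 12 further weeks.

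**Assumed inputs, not in the documents.** Two-sided 5% level; single-day intraclass correlation (ICC) of 0.4 to 0.6; independent noise from day to day; the same true difference between arms whatever the window.

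**Step 1: share of the record used.** Total days = 24 × 7 = 168, or 84 per period.

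- One day at each control visit: 2/168 = 1.2% used.
- Seven days at each: 14/168 = 8.3% used.
- Fourteen days at each: 28/168 = 16.7% used.
- The whole preceding period at each: 168/168 = 100% used.

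**Step 2: variance of a k-day mean**, relative to a single day: V(k) = ICC + (1 − ICC)/k.

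| ICC | V(1) | V(7) | V(84) | V(1)/V(84) | V(7)/V(84) |
|---|---|---|---|---|---|
| 0.4 | 1 | 0.486 | 0.407 | 2.46 | 1.19 |
| 0.5 | 1 | 0.571 | 0.506 | 1.98 | 1.13 |
| 0.6 | 1 | 0.657 | 0.605 | 1.65 | 1.09 |

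**Step 3: power.** With 20 per arm and a t-test, the difference detectable with 80% power is 0.909 SD of the 84-day mean. With a k-day window the same difference becomes 0.909/√(V(k)/V(84)) SD units.

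- Seven days: 0.909/√1.19 = 0.83 (ICC 0.4) to 0.909/√1.09 = 0.87 (ICC 0.6). Power is 73% to 77%.
- One day: 0.909/√2.46 = 0.58 to 0.909/√1.65 = 0.71. Power is 43% to 59%.

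In terms of sample size, one day is equivalent to 20/2.46 = 8 up to 20/1.65 = 12 men per arm analysed on the 84-day mean. The detectable difference grows by a factor of √1.09 to √1.19 (4% to 9%) with seven days. With one day it rises from 0.909 to between 1.17 and 1.42 SD. With a full 84-day look-back the ratio is 1 and nothing is lost.

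**The case against.** A reader might infer that the plan throws away most of the activity data and never compares average activity. The documents do not establish this. The outcome list itself separates activity, measured throughout, from the visit-based outcomes. A comparison of daily activity at a control visit can mean a summary of the daily values recorded up to that visit. On that reading every day is used. The visit wording may also attach mainly to quality of life, which shares the sentence. The secondary outcome on change after supervision draws on monitor data beyond the first visit.

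A reader might also infer that the first-visit value mixes supervised and post-supervised days. That needs a window straddling the visit, and the plan describes none. The first visit follows the 12 weeks and the second phase starts after it, so a look-back window need not mix the two.

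The 43-59% power figure needs a single visit day, which the plan does not state, and an ICC with no source in the documents. The exercise programme is progressive, so the effect late in a period may differ from the average effect. Section 5 also gives special attention to continued exercise at the second visit, so late activity is a legitimate interest.

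All of this stands as a limit on the size of the problem. It does not remove it. One sentence that can mean 1, 7 or 84 days leaves the primary quantity undefined. Its plain reading does not match the stated goal.

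**Conclusion.** The concern holds as a mismatch between goal and analysis with an undefined summary. It does not hold as proof that data are discarded. On the literal reading, most of the record goes unused and average activity over the supervised period is not estimated. On the 12-week look-back reading, there is no loss. The documents do not settle which applies.

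Under the stated assumptions, the cost ranges from none (84 days), through a modest loss with a 7-day window, to a serious one with a single day. These figures illustrate sensitivity to the window and do not predict this trial's power. The analysis should be specified, because it concerns a primary outcome and the change is cheap.

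**What to change.** In the statistical analysis paragraph of section 7:

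- Define each man's activity as his mean daily MET over all valid monitor days in weeks 1-12. Use this for the primary comparison.
- Define the same mean over weeks 13-24 as secondary. Together with the first mean it supplies the listed change-after-supervision outcome.
- Fix a valid-day rule before the data are examined.
- Compare arms on these means, adjusted for the baseline activity value that the plan already lists. First confirm that it is recorded before randomisation. Section 5 does not say when monitors are first worn. If baseline is not recorded before randomisation, compare without that adjustment.
- A look-back summary before the second control visit may be kept as a further secondary measure, since continued activity is a stated interest.

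The cost is SAP wording, a valid-day rule and a little data handling. The follow-up recordings are already planned.

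### The pilot is meant to estimate effect sizes, but section 7 plans only medians compared by Mann-Whitney or t-test and no measure of precision for any primary outcome

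*Combined protocol and SAP*

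**What the plan says.** Section 3 (Study setting) states the aim: "This will be a pilot study to estimate effect sizes in Finnish population to inform further larger trial". The target is 40 men, and "no power calculation is performed yet". Section 5 gives 1:1 allocation.

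Section 7 lists the primary outcomes:

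- activity: "Daily total activity, measured during the entire course of study";
- lipids: "Fasting plasma cholesterol, LDL, HDL and triglycerides, measured at baseline and again at the 1st and 2nd control visits";
- glucose: "Fasting plasma glucose and glycated haemoglobin (HbA1C), measured at baseline and again at the 1st and 2nd control visits";
- overall and prostate cancer-specific quality of life from two EORTC questionnaires, at the same three time points.

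Under Statistical analysis in the same section, medians of activity and quality of life "at baseline and at each control visit are compared with either Mann-Whitney U-test" or Student's t-test, depending on whether the data look normal. For the laboratory outcomes: "Difference in medians of plasma lipid parameters and glucose parameters are analyzed similarly".

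The rest of the analysis text deals with time-to-event outcomes, by Kaplan-Meier, log-rank and Cox methods. The documents mention no confidence interval for any outcome.

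**The concern.** A pilot run to estimate effect sizes needs two things from each primary outcome: an estimate of the difference between arms and a statement of how precise it is. Section 7 provides for the first in part (medians by arm, and a named difference in medians for lipids and glucose) and for the second not at all. The only inferential step it specifies is a two-sample test.

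A test result does not carry the missing information. A large p-value in a trial of this size is compatible with no effect and also with a substantial one. The planners of the larger trial would have a point estimate, or only a pair of medians, with nothing to show how far the true effect could lie from it. They could drop an outcome because its test was not significant, or size the next trial on an estimate that is much less certain than it looks.

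**Working it through.** The documents contain no power or precision calculation, so there is no planned figure to reproduce. The check has two parts.

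**1. Number of comparisons.** From the primary outcome list in section 7:

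| Domain | Variables |
|---|---|
| Daily activity | 1 |
| Total cholesterol, LDL, HDL, triglycerides | 4 |
| Fasting glucose, HbA1c | 2 |
| Two questionnaires, one score each (minimum) | 2 |
| **Total** | **9** |

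- Post-baseline: 9 × 2 control visits = 18.
- With the baseline tests that the same sentence plans: 9 × 3 = 27.

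The count depends on two readings. Section 7 does not say which questionnaire scores will be compared, and more than one per instrument would raise it. Activity is recorded continuously but compared by visit according to the analysis text; a single whole-course comparison would give 17 post-baseline. The secondary outcome "Change in daily activity after the end of supervised group exercise intervention" is a change after supervision ends, which is a different quantity and is not counted here. No interval is planned for any of these comparisons.

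**2. Precision that the plan leaves unreported.** Inputs: 40 men allocated 1:1, so n = 20 per arm if all are evaluable. The documents give no dropout rate, so losses of 10% and 20% (18 and 16 per arm) are assumptions. They give no SDs either, so results are in SD units.

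Half-width of the 95% interval for a difference in means = t(0.975, 2n−2) × √(2/n):

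| n per arm | t quantile | √(2/n) | Half-width (SD) |
|---|---|---|---|
| 20 | 2.024 | 0.316 | 0.64 |
| 18 | 2.032 | 0.333 | 0.68 |
| 16 | 2.042 | 0.354 | 0.72 |

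For a Hodges-Lehmann shift (the estimate that goes with the Mann-Whitney test), simulation with normal data and 20 per arm gives a mean half-width of about 0.66 SD, so the picture is much the same.

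Worked case, 20 per arm, assumed observed difference 0.5 SD:

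- t = 0.5 / 0.316 = 1.58 on 38 degrees of freedom, two-sided p = 0.12;
- 95% interval = 0.5 ± 0.64 = −0.14 to 1.14 SD.

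The test says only that the result is not significant at the conventional level. The interval says that the data are compatible with anything from a small disadvantage to a very large benefit, which is what the planners of the next trial need to know.

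**The case against.** **Effect measures are planned.** Section 7 compares medians and names a difference in medians for the laboratory outcomes. It mentions no p-value, alpha or significance threshold. A reader might infer that the plan will report nothing but p-values; the text does not support that. What is missing is precision, not every effect measure.

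**Exploratory status is already implied.** Section 3 calls the trial a pilot, smaller than earlier studies and without a power calculation. Section 2 states a directional hypothesis across the outcome domains, but that is an expectation and not a success rule. This stands: an explicit exploratory sentence in section 7 would help, but its absence is not the defect.

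**The number of tests is not itself a fault.** A reader might go on to infer that 18 or more tests create a false-positive problem that needs correction. The documents do not support this. Nowhere do they say that any one significant result makes the trial positive, they give no alpha, and a pilot aimed at estimation does not require formal multiplicity control. The count shows only how widely the missing intervals apply.

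**Intervals could be computed later.** This is true: silence does not forbid them, and the same data would yield them, so nothing is irretrievably lost. But the plan does not commit to them, and it leaves the estimator open to a normality check made after the data are in.

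**Conclusion.** The concern holds in a limited form. The stated aim is to estimate effect sizes, and the primary analysis as written does not show how uncertain those estimates will be. This applies to all nine or more primary variables at both control visits.

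The uncertainty is large: about ±0.64 SD for a mean difference with 20 evaluable men per arm, and ±0.72 SD with 16. These widths rest on equal arms, a common SD and a t-based interval; the losses and the 0.5 SD example are assumptions. The widths follow from the sample size and would be the same whether reported or not. The defect is that the plan does not commit to showing them.

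The point is worth acting on because the remedy is cheap and goes to the trial's purpose. It does not mean that the planned tests are invalid, that the sample is too small for a pilot, or that the protocol makes confirmatory claims.

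**What to change.** In section 7, under Statistical analysis:

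1. State that the main result for each primary outcome at each control visit is the between-arm difference with a 95% confidence interval, and that any p-value is secondary.
2. Name one estimator per outcome in advance and use it at both control visits: for example a mean difference, or a Hodges-Lehmann shift for outcomes expected to be skewed. Do not let a normality check choose it visit by visit, because the two visits of one outcome could then be on different scales. Note in the text that a Hodges-Lehmann shift is not in general the difference in medians.
3. As a clarification, add that all primary comparisons are exploratory and that all will be reported whatever their result.

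**Cost.** No new data, visits or participants are needed. There is slightly more analysis work and a small change of effect measure away from medians. The intervals will be wide, and most will include zero when the observed difference is below about 0.64 SD. With 20 per arm that is a strict rule only for the t interval: in simulation with normal data and an assumed true effect of 0.5 SD, about 4% of trials below that value gave a Mann-Whitney p below 0.05, and so a Hodges-Lehmann interval that excludes zero.
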